Appendix A: Demographics:

Includes date of birth, gender, race, education, marital and employment status, area of residence, presence of any co-morbid conditions, medical history, alcohol use, tobacco use, and dietary habits. To be completed by the patient –approximate time for completion is 3 to 5 minutes.

Appendix B: Vanderbilt Head and Neck Symptom Survey version 2.0 (VHNSS 2.0)

This 61-item instrument has been developed specifically to measure acute and late symptoms in HNC patients. Items are summed to provide a total score as well as 13 domain scores. Studies have reported good internal consistency for the total VHNSS scale ($\alpha=0.94$) and five subscales (i.e., swallow, nutrition, mucous/dry mouth, pain, voice) (α s=0.77-0.93), and adequate convergent and divergent validity. Mean scores on each VHNSS subscale can range from 0 (none) to 10 (a lot). Higher scores reflect greater symptom burden. To be completed by the patient – approximate completion time less than 10 minutes.

Appendix C: Pain Survey:

Patients will be asked to complete a pain survey that will allow the healthcare providers and study investigators to appropriately assess and monitor the patient's pain throughout the study.

Patients will be asked to mark their **average pain** , **current pain** and their **worst pain** every week on a scale from 1-10, 10 being the worst pain they have ever felt. They will also be asked to document the number of rescue doses used each day.

Appendix D: Compliance Diary:

Patients on the gabapentin arm will be asked to maintain a complete a survey to document compliance with gabapentin. The reason for missed doses will be captured.

Appendix E: Profile of Mood States-Short Form: The Profile of Moods states is a 37-item scale is composed of six subscales: depression, vigor, confusion, tension, anger and fatigue. Cronbach's alphas ranged from .78 to .91. It correlates will with other measures of mood and physical function, yet is has the benefit of a short administration time.

Appendix F: Neurotoxicity Rating Scale (NRS): The NRS is a 37 item instrument whose items reflect symptoms associated with neurotoxicity of medical treatment [41] Participants rate the severity of all of the 37 item, 5 point Likert-like scale that rates neuropsychiatric symptoms on a scale of “not present” to “extremely severe.”

Appendix G: Quality of Life QOL will be measured using Cantril's Ladder, a single item self-anchoring scale ([42]; [43]). The measure asks patients to rate their current quality of life on a scale ranging from 0 to 10, with higher scores indicating better overall quality of life. Discriminant validity has been supported by significantly lower scores in patients with rheumatoid arthritis than in healthy controls ([44]). Construct validity has been supported by a positive relationship between scores on to social role retention in survivors of bone marrow transplantation ([45]). A 5 item domain-specific QOL questionnaire will also be used.

Appendix H: Disease and Treatment Data Form – Data related to the patient's cancer and treatment including diagnosis date, location, stage of disease, surgical treatment, medical oncology treatment, and radiation oncology treatment will be determined by medical record review at the time of the study visit and will be completed by study nurse or study providers.

Appendix I: Studies to be Done:

	Baseline¥	Week 1	Week 2	Week 3	Week 4	Week 5	Week 6 *	Week 7 *	1,2 3 Months post tx
Study Visit	X	X	X	X	X	X	X	X	X
Chemoradiation Teaching	X								
Foundations of Oral Care	X								
Foundations of Pain Management	X								
Randomization	X								
Gabapentin Arm 2 Only		X	X	X	X	X	X	X	X
Mucositis Grading	X	X	X	X	X	X	X	X	X
Demographic Survey	X								
VHNS Version 2.0		X	X	X	X	X	X	X	X
Pain Survey		X	X	X	X	X	X	X	X
Compliance Survey Arm 2 Only		X	X	X	X	X	X	X	X
Neurotoxicity Scale	X						X		X (month 3 only)
POMS	X						X		X (month 3 only)
QOL	X						X		X (month 3 only)

Disease and Treatment Form	X								
----------------------------	---	--	--	--	--	--	--	--	--

‡ All baseline assessments must be done within 4 weeks before starting concurrent chemoradiation.

* Weekly assessments will continue until the completion of chemoradiation which may vary between 5 and 7 weeks.

An End of Treatment Visit will be conducted 2 weeks after Chemoradiation therapy

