5.0 Study Procedures

5.1 Chemoradiation:

Chemotherapy and radiation will be instituted per standard of care. There will be no alterations in standard of care as a result of participation in this study. Disease treatment related data will be obtained through chart review after the completion of therapy.

5.2 Study Treatment:

Patients will be randomized to Arm 1 (Usual Care) or Arm 2 – (Usual Care plus Gabapentin).

Arm 1: Usual Care:

Usual care will include the following:

1. Oral health measures including brushing, flossing, and the use of fluoride toothpaste
2. Oral rinsing with baking soda and salt water gargles every 2-3 hours while awake
3. Miracle mouthwash formulated to include topical lidocaine, Benadryl, and Maalox;
4. Nonsteroidal anti-inflammatories around the clock to treat pain and inflammation
5. Opioid analgesics to include a fixed and breakthrough medication.

Patients will undergo an education session at the beginning of treatment to review foundations of oral care and pain management.

Arm 2: Usual Care plus Gabapentin.

Patients will receive all measures for Arm 1 **PLUS** Gabapentin. Gabapentin will be dose escalated using a slow escalation schema to minimize the sedating effects of medication and avoid undue toxicities:

- Week 1: Gabapentin 100 mg PO 3 times a day
- Week 2: Gabapentin 300 mg PO 3 times a day.
- Week 3: Gabapentin 600 mg PO 3 times a day.
- Week 4 onward: Gabapentin 900 mg PO 3 times a day.

The highest tolerated dose of gabapentin will continue throughout treatment. Missed doses, though regrettable, are part of any patient-administered medication and will not be considered deviations for this study as we are studying practical efficacy. After completion of therapy, mucositis is expected to resolve at a variable rate (1 to 3 months post treatment). Gabapentin will be continued until mucositis resolves **and** pain subsides. Patients will be weaned off opioids prior to initiation of gabapentin de-escalation. Once opioids have been weaned, de-escalation of gabapentin will be initiated. Since the rate at which patients can be weaned of pain medications is variable, de-escalation will be managed by the treating physician. Abrupt discontinuation of gabapentin will be discouraged in order to avoid symptoms related to withdrawal.

5.3 Dose Modifications:

Prior to each dose escalation, patients will be assessed for side effects related to gabapentin.

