- Patients who are tolerating the current dosing schedule will undertake an escalation to the next dose level.
- If patients have mild to moderate side effects related to gabapentin, no further dose escalation will be undertaken
- If patients develop severe side effects attributable to gabapentin, gabapentin will be held until the side effects have totally resolved and then restarted at the last known tolerated dose level.
- Although rare, severe mood alterations and suicidal thoughts have been associated with this agent. Should patients experience these symptoms, gabapentin will be permanently discontinued.

5.4 Route of Administration:

Gabapentin is usually taken orally. Gabapentin may also be crushed and given via feeding tube if the patient is unable to swallow the tablet.

5.5 Pain Management:

Pain management for tumor and treatment related toxicities will be at the discretion of the treating physician. Opioid and adjuvant use will be documented for study purposes. At the completion of study, patients on Arm 1 may be started on gabapentin if they have uncontrolled mucositis associated pain. For patients assigned to Arm 1, the treating physician will manage the utilization of gabapentin during the post-treatment phase

5.6 Study Visits:

In order to minimize inconvenience to patients under study, study visits will coincide with scheduled treatment. This may introduce a degree of variability in the timing of weekly visits and follow-up visits which will be considered acceptable except in cases where explicit visit timing is dictated elsewhere in the protocol. Weekly on treatment visits that are more than 1 week late will be considered missing.

Baseline:

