Prior to initiating therapy, patients will undergo education sessions with study staff. The educational intervention will include a discussion of oral health foundations as well as a discussion of pain management. This education is standardly applied to all VUMC patients undergoing radiation therapy for HNC and will not be otherwise documented. In addition, patients will also be given written material to review. Patient will be given a pain diary and instructed on its use. Baseline pain medication use will be documented. Patients will complete the demographic survey. Patients randomized to gabapentin will be given a prescription for gabapentin with dose escalation as noted in the treatment section. Patients who do not have insurance or who are unable to afford gabapentin will be provided with medication from the indigent pharmacy. All baseline assessments must be done within 4 weeks of starting concurrent chemoradiation.

Weekly On Treatment Visits:

Starting with the initiation of concurrent chemoradiation, patients will be evaluated on a weekly basis. The evaluation will include:

- 1) review of the weekly pain survey
- 2) for patients on gabapentin (Arm 2) --we will review their compliance log and identify any barriers to compliance and strategies to improve their compliance
- 3) adjustment of pain regimen
- 4) completion and review of the Vanderbilt head and neck symptom survey
- 5) mucositis grading.

End-of-Treatment Visit:

Patients will undergo an evaluation at their final radiotherapy visit or within 2 weeks after. This will include the following:

- 1) review of the monthly diary survey
- 2) for patients on gabapentin (Arm 2) --we will review their compliance log and identify any barriers to compliance and strategies to improve their compliance

- 3) adjustment of pain regimen
- 4) completion and review of the Vanderbilt head and neck symptom survey
- 5) mucositis grading.

6.0 Study Measures:

6.1 Mucositis Grading:

Patients will have an oral exam twice a week as part of standard of care. Mucositis will be graded based on the World Health Organization criteria. Mucositis assessments will be done by trained study staff.

6.2 Patient Reported Outcome Measures:

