10.0 Statistical Considerations and Sample Size Justification

General evaluation and analysis plan: Statistical software will be used to summarize the data collected and to test study hypotheses. Intent-to-treat principles will be used for all analyses. An interim analysis of the VHNSS pain scores will be conducted when 50% of the participants have been randomized and have completed the 3 month follow-up period. To maintain the final overall alpha of $P < 0.05$, the Haybittle-Peto approach will be used: the trial will be stopped at that point if the symmetric stopping boundaries of $P < 0.001$ are met. The interim analysis will only be used for this purpose, i.e. no futility analyses will be conducted.

Management of Missing Data: In-depth investigations of patterns of missing data will be undertaken. Given the longitudinal nature of this study, we expect two types of missing data: 1) randomly missing responses to items within the self-report measures (e.g., VHNSS) and 2) non-randomly missing lost-to-follow up (LTF) assessments. Our proposed sample size accommodates up to 30 LTF (i.e., up to 20% of those randomized) to arrive at a total analysis sample size of 120. Randomly missing item response data will be handled via protocols specified by the instrument developers. When there is no specified protocol, if the participant has completed 75% or more of the items on a particular instrument, prorated scores for that instrument will be generated using available item responses. Non-randomly missing data will be assessed to determine whether it provides clinically important information and implications for generalizability of findings. All efforts as outlined by White et al. (2011) for handling missing outcome data in an RCT-ITT analysis will be conducted.

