Appendix F: Neurotoxicity Rating Scale

Directions: Place an X at the level of severity of each symptom.

	Not present	Mild	Moderate	Severe	Extremely severe
1. Anxiety					
2. Health worries					
3. Sadness/depression					
4. Restlessness					
5. No interest in people					
6. No interest in activities					
7. Difficulty making decisions					
8. Strange thoughts					
9. All-over sick feeling					
10. Difficulty getting to sleep					
11. Difficulty staying asleep					
12. Sleeping too much					
13. Nausea					
14. Vomiting					
15. Loss of appetite					
16. Tiredness/fatigue					
17. Distractibility					
18. Body aches					
19. Joint pain					
20. Other pain					
21. Episodes of confusion					
22. Word-finding problem					
23. Memory problems					

24. Irritability					
25. Decreased motivation					
26. Hallucinations					
27. Lack of emotion					
28. Mood swings					
	Not present	Mild	Moderate	Severe	Extremely severe
29. Tension					
30. Slowed movements					
31. Tremor/shakiness					
32. Walking problems					
33. Vision problems					
34. Bowel/blader problems					
35. Loss of interest in sex					
36. Fever					
37. Headaches					

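### POMS, NRS and QOL are scheduled on treatment only at week 6, so a 5-week chemoradiation course has no value between baseline and month 3

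*Combined protocol and SAP*

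**What the plan says.** The calendar appears twice, once within section 6.2 (Appendix I: Studies to be Done) and once at the end (Appendix I: Study Procedure Calendar). In both, the rows for the Neurotoxicity Scale, POMS and QOL carry three marks: baseline, week 6, and month 3 of the post-treatment column. Weeks 1 to 5 and week 7 are blank. Weeks 6 and 7 bear an asterisk, explained in both copies: "Weekly assessments will continue until the completion of chemoradiation which may vary between 5 and 7 weeks".

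Section 5.6 adds an end-of-treatment visit: "Patients will undergo an evaluation at their final radiotherapy visit or within 2 weeks after". Its content is the diary, the compliance log, the pain regimen, the VHNSS and mucositis grading. POMS, NRS and QOL are not on the list.

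Section 6.2 has the study nurse give whatever questionnaires are appropriate at each visit and counts the patient-reported measures among the outcomes of interest. It says of one of the three forms: "NRS is a 37 item instrument whose items reflect symptoms associated with neurotoxicity of medical treatment".

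On gaps in the data, section 10.0 states: "Given the longitudinal nature of this study, we expect two types of missing data". The two types are item responses missing at random and assessments lost to follow-up.

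**The concern.** The plan puts its single on-treatment measurement of mood, neurotoxicity and quality of life in a week that, by its own footnote, some patients will not reach. For them the value is lost by design. It is not lost through withdrawal or an incomplete form, so the missing-data section does not anticipate it.

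What is at stake is any description or comparison of the arms on these three instruments during treatment. It would rest on 6- and 7-week courses only. The missing value cannot be rebuilt afterwards: the POMS form asks about the preceding two weeks and the QOL items about the preceding week, so a month-3 answer does not reach back to the treatment period.

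**Working it through.** The plan gives no figure on this point to reproduce. The check is a reading of the schedule plus simple arithmetic.

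**Inputs.** Course length 5 to 7 weeks (Appendix I footnote). Forms at baseline, week 6 and month 3 after treatment (Appendix I, both copies). Baseline up to 4 weeks before the start (Appendix I footnote and section 5.6). Assumption: 3 months = 13 weeks, counted from the end of chemoradiation.

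**Step 1: values by course length.** Month-3 value, in weeks after the start = course length + 13.

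| Course | On-treatment values | Month-3 value (weeks after start) | Gap before the month-3 value |
|---|---|---|---|
| 5 weeks | 0 of 1 | 5 + 13 = 18 | from baseline: 18 + 0 to 18 + 4 = 18 to 22 weeks |
| 6 weeks | 1 of 1 | 6 + 13 = 19 | from week 6: 19 − 6 = 13 weeks |
| 7 weeks | 1 of 1 | 7 + 13 = 20 | from week 6: 20 − 6 = 14 weeks |

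A 5-week course thus has 2 of its 3 planned values, and the one it lacks is its only on-treatment value.

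**Step 2: does another provision recover it?**
- End-of-treatment visit: for a 5-week course it falls between week 5 and week 5 + 2 = 7. The timing would serve, but the listed content leaves out the three forms.
- Section 6.2, appropriate questionnaires: this refers the nurse back to a schedule and gives no rule for moving the week-6 set.
- Section 5.6 timing tolerance: it accepts some variation and treats a weekly visit as missing only when it is more than a week late. That covers late visits. It does not bring a week-6 form forward to week 5.

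None of the three schedules the forms.

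**Step 3: can month 3 stand in?** Section 5.2 expects mucositis to clear 1 to 3 months after treatment. Opioids are then weaned, and after them gabapentin. Some Arm 2 patients may therefore be off the drug at month 3, while others still take it. Section 5.5 allows Arm 1 patients with uncontrolled mucositis pain to start gabapentin once the study is complete and places that use in the post-treatment phase. Section 1.6 ends participation when therapy ends, so this may happen before month 3. Month 3 is thus a weaker contrast between the randomized treatments than a value taken on treatment.

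**Step 4: illustration only.** The share of 5-week courses is not stated. Suppose it were 5%, 10%, 20% or 30% of the 120 planned completers, equal in both arms. On-treatment values would remain for 114, 108, 96 or 84 patients. The standardized difference detectable with 80% power at two-sided 0.05 is (1.960 + 0.842) × √(2/m), with m patients per arm:
- all 120 (m = 60): 0.51
- 114 (m = 57): 0.52
- 108 (m = 54): 0.54
- 96 (m = 48): 0.57
- 84 (m = 42): 0.61

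No such test is planned. The figures show only that the loss of precision would be modest unless short courses were common.

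**The case against.** The strongest reply is that nothing planned is lost. Section 2.0 names no outcome based on POMS, NRS or QOL, and section 10.0 names no analysis of them. Aim 3 uses grade 3 or 4 adverse events and discontinuation. The general symptoms of Aim 4 have their own subscale in the VHNSS, which is given weekly. The number of 5-week courses is unknown, and hypotheses 1.1 and 1.2 are themselves set at week six, so the investigators evidently expect most patients to get there. A sensible nurse could also give the forms at the end-of-treatment visit.

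Most of this stands and limits the weight of the point. It does not remove it: the plan collects these forms as outcomes of interest, and what a sensible nurse could do is not scheduled.

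A reader might go further in two directions that the documents do not support.

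- *That neurotoxicity at the full dose escapes observation.* The dosing plan reads "Week 4 onward: Gabapentin 900 mg PO 3 times a day", and a 5-week course ends soon after. But gabapentin does not stop with chemoradiation: section 5.2 continues it until mucositis and pain have settled, and both calendars mark it in the post-treatment column. CTCAE toxicities are recorded at every study visit.
- *That the mood stopping rule cannot be applied.* Section 5.3 notes that "severe mood alterations and suicidal thoughts have been associated with this agent" and continues: "Should patients experience these symptoms, gabapentin will be permanently discontinued". That rule does not depend on the POMS. Side effects are assessed before each escalation, toxicities and adverse events are recorded at every visit, and the weekly VHNSS asks about sadness and anxiety. The nurse's own toxicity record is not among the appendices, so nothing can be said about what it prompts for.

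**Conclusion.** The gap is real and small. Followed exactly, a 5-week course has no POMS, NRS or QOL value from baseline until about 18 weeks after the start of chemoradiation (18 to 22 weeks after baseline). This rests on the calendar as printed, identically in both copies for these rows, and on 3 months being 13 weeks.

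Its trial-level size cannot be stated, because the share of 5-week courses is not given. The consequence is limited to supportive mood, neurotoxicity and quality-of-life data. A reader might infer damage to Aim 1 or Aim 3, or bias between the arms. The documents show neither. VHNSS scores and adverse events are still collected weekly in these patients. Chemoradiation follows standard of care in both arms (section 5.1), so randomization should balance course length on average. The harm is lost data and a narrower population for the on-treatment description. Severity: minor.

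**What to change.** Add one footnote to the POMS, NRS and QOL rows in both copies of Appendix I: give these forms at week 6 or in the last treatment week, whichever comes first. State that the result is summarized as one on-treatment time point, and record the actual treatment week.

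No new visit or form is needed. A 5-week patient would complete 37 + 37 + 6 = 80 items in the last treatment week, the same set that other patients already complete at week 6. The downside is that the value comes from week 5 in some patients and week 6 in others, so the time point is slightly less uniform. That is preferable to having no value, since these data cannot be collected later.

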7.0 Risks of Investigational Agents/Devices (side effects)

Gabapentin:

- >10%
 - **Central Nervous System:** Dizziness (IR 17% - 28%, ER 11%), Drowsiness (IR 19%-21%; ER 5%), Ataxia (1% to 13%), Fatigue (11%)
- 1-10%
 - **Cardiovascular:** Peripheral edema (IR: 2% to 8%; ER: 4%), vasodilatation (1%)
 - **Central nervous system:** Hostility (children 5% to 8%), tremor (7%), emotional lability (children 4% to 6%), hyperkinesia (children 3% to 5%), headache (ER: 4%; IR: 3%), abnormality in thinking (2% to 3%; children 2%), abnormal gait (2%), amnesia (2%), depression (2%), nervousness (2%), pain (ER: 1% to 2%), hyperesthesia (1%), lethargy (ER: 1%), twitching (1%), vertigo (ER: 1%)
 - **Dermatologic:** Pruritus (1%), skin rash (1%)
 - **Endocrine & metabolic:** Weight gain (IR: Adults and children 2% to 3%; ER: 2%), hyperglycemia (1%)
 - **Gastrointestinal:** Diarrhea (IR: 6%; ER: 3%), nausea and vomiting (3% to 4%; children 8%), xerostomia (IR: 2% to 5%; ER: 3%), constipation (IR: 1% to 4%; ER: 1%), abdominal pain (3%), dyspepsia (IR: 2%; ER: 1%), dry throat (2%), dental disease (2%), flatulence (2%), increased appetite (1%)
 - **Genitourinary:** Impotence (2%), urinary tract infection (ER: 2%)
 - **Hematologic & oncologic:** Decreased white blood cell count (1%), leukopenia (1%)
 - **Infection:** Infection (5%)
 - **Neuromuscular & skeletal:** Weakness (6%), back pain (IR: 2%; ER: 2%), dysarthria (2%), limb pain (ER: 2%), myalgia (2%), bone fracture (1%)
 - **Ophthalmic:** Nystagmus (8%), diplopia (1% to 6%), blurred vision (3% to 4%), conjunctivitis (1%)
 - **Otic:** Otitis media (1%)
 - **Respiratory:** Rhinitis (4%), bronchitis (children 3%), nasopharyngitis (ER: 3%), respiratory tract infection (children 3%), pharyngitis (1% to 3%), cough (2%)
 - **Miscellaneous:** Fever (children 10%)

8.0 Reporting of Adverse Events or Unanticipated Problems involving Risk to Participants or Others

8.1 Safety Monitoring:

Participants will be educated regarding signs and symptoms related to adverse events (AEs) requiring urgent or emergent medical care. All AEs grade 3 or higher will be documented, reviewed by [name]. Any contributing factors will be reviewed, and strategies to prevent further complications will be developed and implemented. [name] will meet with study staff annually to evaluate any other safety concerns. AEs will be graded using CTCAE criteria 4.0. All unexpected grade 3, 4 or 5 AEs possibly or probably related to study drug will be reported to the IRB.

Data Safety Monitoring Board:

Four experts will be proposed for the DSMB members. The DSMB members must not be co-investigators or consultants, not have been directly involved in protocol development, not have close current or recent affiliations with the study, nor supervise persons who are directly involved in the study. We will make effort to include at least one representative with expertise in biostatistics, clinical trials methodology, and head and neck oncology.

The DSMB will oversee and monitor the activities related to implementing the study to ensure the safety of participants, adherence to the study protocol, overall performance of the trial components, integrity of data, and security of data management. The DSMB will meet annually, at the time of interim analysis and on an as-needed basis if significant issues arise that impact the study participants or any study activities. For each DSMB meeting, progress reports will be prepared and provided to DSMB members by the PI and mentor. The DSMB will prepare an annual safety report, summarizing the efforts and findings through the annual monitoring.

